10. DATA ANALYSIS AND CONSIDERATIONS

10.1 Sample Size Justification and Primary Clinical Effect Analysis

The sample sizes justification is based on the combination of the pilot data that we have previously observed ([name] Unpublished) and results based on Schweizer et al. (2012). Two main outcomes, MoCA and MMSE, were compared by Schweizer et al (2012) and their validity was compared. The two measures have slightly different cut-offs for defining impairments (MoCA score <26 and MMSE score <27). In this study we will use MoCA as a primary outcome measure. Based on published data, MoCA has mean (SD) of 25.4 (2.8) with n=32. In our pilot data with small sample sizes, we observed an overall mean of 24.6 (5.4) with n=47. The separate group means were 26.4 (2.3) with n=25 and 22.7 (7.0) with n=22 in the treatment and control arms, respectively. Because the two groups were heterogeneous, we assume SD=2.5 in treatment group and SD=7.0 in control group. As hypothesized and as documented in the preliminary data, MoCA is higher in the treatment arm than in the control arm, and so we will use one-sided test procedures. The study design is that of a two group, multicenter randomized clinical trial.

Table S1: Sample sizes based on having alpha=5% and SD1=7.0 and SD2=2.5 to detect 3 unit (effect size=0.5 SD) using one-sided two-sample t test with unequal variances.

Power	N1	Total N
80%	40	80
85%	46	92
90%	54	108

Given the number of centers participating, we plan to enroll 40 evaluable subjects in each arm. Assuming 8 centers, a sample size of 80 would be realized by recruiting 10 per center. Note that we need to balance the number of treatment and controls to be equal at each center, but not necessarily having equal number of subjects at each center. However, the numbers in the tables do not adjust for loss to follow up, drop outs, the ability to adjust for covariates, or for the loss of degrees of freedom for the centers in a test or model. The discussion below addresses further aspects of the sample size consideration.

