Based on a desired total of 40 patients per arm, and an assumed dropout rate of 10%, the trial would require 44 patients in each arm for a total enrollment plan of 88 patients distributed over 8 sites, or on average 11 patients per site. There are multiple covariates that may confound the findings and this needs to be addressed in the design of the study. The primary factors are: center, risk associated with anterior communicating artery (ACoA) aneurysm location (1 versus others), age (≤ 70 versus > 70) and sex. The other factors are: fever (yes, no), transfusion (yes, no), vasospasm (yes, no). Due to limited resources only primary factors (ACoA, group and sex) will be considered to balance the allocation of treatment and control in 1:1 ratio. Thus, the randomization will be balanced within each of 6 strata. Advanced age will be controlled for by eliminating enrollment for patients over 70 years. Effect of the remaining factors will be addressed in the multi-variate model.

We will also compare the frequency of severe cognitive impairment (MoCA ≤ 20) in the two arms. Previous data demonstrated a rate of 0% (0/25) severe cognitive impairment in the heparin treatment group and approximately 32% (7/22) in the control group. In our currently planned study, we will assume a 5% rate of severe cognitive impairment in the heparin treatment group and a 32% rate of severe cognitive impairment in the control group. This will also allow a demonstration of power = 80% with alpha at 0.05 for our previously calculated sample sizes ($n_1=40$ and $n_2=40$) using a two-sample one-sided binomial test. This binomial calculation provides a second sample size estimate that supports our previous estimate of needing 40 patients per group. Therefore the final sample size estimation will be placed at a total of 88 patients to account for a 10% dropout rate leaving a final number of patients available for primary outcome analysis of 80 patients. Drop-out will be monitored during the enrollment process. If we approach 8 patients lost to follow-up then additional enrollments (beyond 88) will be considered if funding is available.

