10.2 Correlation Analysis

In addition to testing the correlations with one sample (treatment + control groups together), we can identify an absolute correlation of 0.27 from no correlation at the same design parameters. When comparing within each treatment group the detectable correlation will be at least 0.37. For comparing correlations between two groups (treatment and controls), the difference of detectable correlation is at least 0.50 at the same design parameters. In all three types of effect size calculations, the detectable effect sizes are moderate-to- large (Cohen, 1988). Note that sample size justification does not take into account the multiple but correlated outcomes within same subjects. Sample size calculation is based on methods described in Chow et al (2008) and Cohen (1988).

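### The power for MoCA ≤20 is stated as 80%, but the stated one-sided inputs give about 92–96%, so this is not a second estimate that arrives at 40 per group

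*Protocol*

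**What the plan says.** Protocol section 10.1 sets the sample size with a one-sided Welch t test on the mean 90-day MoCA score. Table S1 gives 80% power at 40 per arm for "alpha=5% and SD1=7.0 and SD2=2.5 to detect 3 unit (effect size=0.5 SD) using one-sided two-sample t test with unequal variances". Allowing for 10% dropout, 40 evaluable patients become 44 per arm, or 88 in total.

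The section then turns to a binary version of the same scale, MoCA ≤20. For planning, "we will assume a 5% rate of severe cognitive impairment in the heparin treatment group"; among controls the assumed figure is 32%. With 40 patients in each arm and a one-sided two-sample binomial test, it states: "This will also allow a demonstration of power = 80% with alpha at 0.05 for our previously calculated sample sizes".

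It draws this conclusion: "This binomial calculation provides a second sample size estimate that supports our previous estimate of needing 40 patients per group". The total of 88 follows in the next sentence as a consequence.

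**The concern.** Every input to the binary calculation is fixed in the text: two rates, alpha, the number per arm, and a one-sided test. The power can therefore be checked directly, and a drop from 32% to 5% is a large effect for 40 per arm. A stated power of exactly 80%, at exactly the size the t test had already given, looks too neat.

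What is at stake is how the sample size is justified. The protocol presents two calculations that meet at 40 per group. If the second, run as described, needs clearly fewer patients, the two do not meet. The reader is then wrongly told that a second endpoint confirms the number, and is also given the wrong power for that endpoint.

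**Working it through.** **Inputs, all from Protocol section 10.1.** p1 = 0.05 (heparin), p2 = 0.32 (control), n = 40 per arm, alpha = 0.05 one-sided. The difference is 0.27 and the mean rate is (0.05 + 0.32)/2 = 0.185.

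**1. Trying to reproduce 80% with the pooled normal approximation.**
- Null standard error: √(2 × 0.185 × 0.815/40) = 0.0868.
- Alternative standard error: √((0.05 × 0.95 + 0.32 × 0.68)/40) = 0.0814.
- Power = Φ((0.27 − 1.645 × 0.0868)/0.0814) = Φ(1.562) = 94.1%.

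**2. Other one-sided methods at 40 per arm.**

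| Method | Power |
|---|---|
| Fisher's exact test, full enumeration | 92.3% |
| Pooled z test, full enumeration | 95.7% |
| Unpooled z, normal approximation | 95.3% |
| Arcsine approximation | 95.7% |
| Continuity-corrected z, pooled approximation | 89.5% |
| Continuity-corrected z, unpooled approximation | 91.4% |
| Continuity-corrected z, full enumeration | 91.9% |

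For the pooled continuity-corrected entry, the numerator loses 1/40: Φ((0.27 − 0.025 − 1.645 × 0.0868)/0.0814) = Φ(1.255) = 89.5%. No one-sided method comes near 80%.

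**3. Patients per arm for 80% power, one-sided.**
- Pooled formula: n = ((1.645 × √(2 × 0.185 × 0.815) + 0.842 × √(0.05 × 0.95 + 0.32 × 0.68))/0.27)² = ((0.903 + 0.433)/0.27)² = 24.5, so 25.
- With continuity correction: (24.5/4) × (1 + √(1 + 4/(24.5 × 0.27)))² = 31.5, so 32.
- Full enumeration: 22 for the pooled z test (80.5%) and 30 for Fisher's exact test (80.1%).

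The range is 22 to 32 per arm, against the 40 it is said to support.

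**4. A possible origin of the figure.** Replacing 1.645 by 1.960 (two-sided) gives 31.3 by the pooled formula and 38.3 with the continuity correction, so 39 per arm. Power at 40 is then 82.1%. This is the variant tried that comes closest to the protocol's statement, and it contradicts the one-sided test named there. Two-sided Fisher's exact test at 40 per arm gives 87.0%.

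**5. The calculation that sets the size.** For Table S1, the standard error is √(49/40 + 6.25/40) = 1.175 and the noncentrality is 3/1.175 = 2.553. The Welch degrees of freedom are 48.8 and the one-sided critical value is 1.677. Power is 80.8%, so Table S1 reproduces at 40 per arm.

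**The case against.** The best defence is that the error is conservative. Power is understated, so 40 per arm is more than enough for this endpoint, and in the plain sense the calculation does support enrolling 40. MoCA ≤20 is listed in the synopsis among the additional exploratory analyses, and the total of 88 rests on the primary endpoint through Table S1. A slip in labelling a two-sided continuity-corrected calculation would explain the number almost fully.

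Most of this stands. A reader might infer that the sample size is left unsupported. It is not, because nothing here argues for more or fewer patients. The labelling explanation is plausible, but the document does not confirm it. If it is right, the named test is wrong instead of the power, and the text still needs correcting. What the defence does not rescue is the specific claim of a second estimate of needing 40 per group, because the calculation as described needs 22 to 32.

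A reader might also carry the suspicion over to section 10.2, where "When comparing within each treatment group the detectable correlation will be at least 0.37", and conclude that the correlation figures were worked out on 44 enrolled patients per arm and ignore dropout. The document does not support that. It gives neither the number nor the method. A one-sided noncentral t calculation at 80% power gives 0.270 with 80 patients and 0.372 with 40, which match the stated 0.27 and 0.37 at the evaluable sizes. Only the between-arm difference of 0.50 sits nearer to 44 per arm by Fisher's z (0.500, against 0.521 at 40), and that gap is too small to build on. There is no case for replacing the correlation figures.

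**Conclusion.** The stated 80% is wrong for the test named. With 5% against 32%, one-sided alpha 0.05 and 40 per arm, power is about 92% (Fisher's exact) to 96% (pooled z), or about 90–92% with a continuity correction. The understatement is 12 to 16 percentage points without the correction and roughly 10 to 12 with it. The calculation shows that 40 per arm exceeds what this endpoint needs. It does not independently arrive at 40.

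This rests only on the rates, alpha, group sizes and sidedness printed in section 10.1. The spread reflects the choice of test, which the protocol's general term for a binomial test leaves open. The consequence is limited to the accuracy of the justification: N = 88, the analyses and the primary comparison do not change.

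**What to change.** Make two text changes in Protocol section 10.1:

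1. Either restate the power for MoCA ≤20 at 40 per arm as about 92–96% and name the test (92.3% for one-sided Fisher's exact, 95.7% for the one-sided pooled z test), or, if a two-sided or continuity-corrected calculation was used, correct the stated sidedness and method and give the matching power (82.1% for the two-sided continuity-corrected approximation).
2. Replace the sentence about a second sample size estimate with a statement that 40 per arm exceeds what this endpoint needs, and that the size is set by the MoCA t test in Table S1.

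The cost is a wording correction. Enrolment, analysis and budget are untouched.

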10.2 Correlation Analysis

In addition to testing the correlations with one sample (treatment + control groups together), we can identify an absolute correlation of 0.27 from no correlation at the same design parameters. When comparing within each treatment group the detectable correlation will be at least 0.37. For comparing correlations between two groups (treatment and controls), the difference of detectable correlation is at least 0.50 at the same design parameters. In all three types of effect size calculations, the detectable effect sizes are moderate-to- large (Cohen, 1988). Note that sample size justification does not take into account the multiple but correlated outcomes within same subjects. Sample size calculation is based on methods described in Chow et al (2008) and Cohen (1988).

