Peak and Overall Plasma and CSF levels of hsCRP at enrollment and, infusion days #2, 4, 6, and 10 compared between groups.

-SECONDARY CLINICAL EFFECT ENDPOINTS

Trail Making Test Parts A&B at 90 (± 10) days post enrollment.

MoCA at 1-year (± 30 days)

Center for Epidemiologic Studies Depression Scale (CES-D) at 90 (± 10) days post enrollment

Return to work status between groups at 90 (± 10) days

SECONDARY EXPLORATORY PRESPECIFIED BIOMARKER OUTCOMES

Plasma and CSF levels of IL-6, TNF- α , P-Selectin, sICAM-1, HMGB-1, MRP8/14 plasma levels at enrollment and infusion day #2, 4, 6, and 10

ADDITIONAL PRE-SPECIFIED

Rate of MoCA ≤ 20 between groups at the 90-day follow-up visit.

**EXPLORATORY
OUTCOME ANALYSES**

In-hospital incidence of any fever ($> 38.3^{\circ} \text{C}$; $\geq 101.0^{\circ} \text{F}$), Incidence of multiple fever episodes (≥ 3), and Mean Daily Fever Burden.

GCS and NIHSS at enrollment and infusion days # 2,4,6,10, discharge and 90 (± 10) days

MoCA at post-enrollment day #1, 6 and 10

Correlation analysis between MoCA scores and inflammatory biomarker levels with and without adjusting for hemorrhage burden (Hijdra Sum Score).

Incidence of moderate and severe Radiographic Cerebral Vasospasm based on a CTA, MRA, or Catheter DSA obtained between PBD # 6-12 as determined by an independent and blinded core imaging lab.

Incidence of TCD criteria for significant vasospasm (velocities $>200 \text{ cm/s}$ and / or MCA / ICA (Lindgaard) ratio >6)

Incidence of TCD criteria for absence of vasospasm (velocities $<120 \text{ cm/s}$)

Incidence of clinical vasospasm requiring rescue therapy (eg, pressors, endovascular treatment)

Incidence of "Delayed Cerebral Ischemia" defined as:

- Symptoms of neurological deterioration (e.g. hemiparesis, aphasia, decreased level of consciousness)
- Symptoms last for more than an hour
- Symptoms are not explained by other physiological processes (e.g., hydrocephalus, hypotension)

CT or MRI evidence of Vasospasm Related Cerebral Infarction on post-infusion (discharge) imaging as scored by an independent and blinded core imaging lab

Global outcome as measured between group ordinal regression analysis of the modified Rankin Scale score at 90-days and 1-year.
Return to work status between groups at 1-year.
Lawton IADLs at 90 (± 10) days
QOLIBRI-OS at 90 (± 10) days and 1-year.
Checklist Individual Strength-subscale Fatigue (CIS-f) at 90 (± 10) days
Barthel Index at 90 (± 10) days and 1-year

**INVESTIGATIONAL

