1.2.2 Secondary Objectives

1. Measure the correlation between blood / CSF levels of inflammatory biomarkers (e.g. hsCRP, IL-6) and cognitive function (MoCA).
2. Demonstrate a reduction in blood / CSF levels of inflammatory biomarkers (e.g. hsCRP, IL-6) in the LDIVH treated subjects compared to controls.
3. Demonstrate a reduction in cerebral vasospasm in the LDIVH treated subjects compared to controls by measuring the proportion of patients in each group who:
 - i. Demonstrate moderately severe or severe angiographic vasospasm by CTA or DSA obtained within the prime vasospasm window
 - ii. Demonstrate moderately severe or severe vasospasm on transcranial Dopplers (TCDs)
 - iii. Demonstrate vasospasm related CT infarctions
4. Demonstrate a reduction in “Delayed Cerebral Ischemia” as defined by the Neurocritical Care Society:
 - i. Symptoms of neurological deterioration (e.g., hemiparesis, aphasia, altered consciousness) presumed to be related to ischemia
 - ii. Symptoms persist for more than one hour
 - iii. Symptoms cannot be explained by other physiological abnormalities
5. Demonstrate a reduction in the need for “rescue therapy” for delayed cerebral ischemia and / or symptomatic cerebral vasospasm
6. Demonstrate a difference between the LDIVH treated subjects and controls in the proportion of patients in each group who:
 - i. Have any fever (Temperature $\geq 38.3^{\circ}\text{C}$ / 101.0°F)
 - ii. Have multiple fevers (≥ 3 fever episodes)
7. Demonstrate a significant difference in “fever burden” between LDIVH treated subjects and control subjects
8. Demonstrate a difference between LDIVH treated subjects and controls in mean Daily Fever Burden during the LDIVH infusion.

9. Demonstrate better clinical outcomes in the LDIVH treated subjects compared to controls with one of the following measures:
 - i. mRS at 90 days and 1-year (Ordinal Regression Analysis)
 - ii. Barthel Index at 90 days
 - iii. Center for Epidemiologic Studies Depression Scale (CES-D) at 90 days and 1-year
 - iv. QOLIBRI-OS at 90 days and 1-year
 - v. Lawton IADLs at 90 days
 - vi. Trail Making Test Parts A&B at 90 days
 - vii. Return to Work Status at 90 days and 1-year
 - viii. MoCA at 1-year
10. Perform Pre-specified Subgroup Analysis of Outcome measures for LDVIH and Control groups using the following subgroup designations:
 - i. Sex (Male versus Female)
 - ii. Admission CT Hijdra Sum Score (<23 versus ≥ 23)

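### The all-patient biomarker–MoCA correlation in 10.2 is not adjusted for treatment arm, so it can absorb the treatment effects; the other two correlation analyses there are unaffected

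*Protocol*

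**What the plan says.** Secondary objective 1 (section 1.2.2) is: "Measure the correlation between blood / CSF levels of inflammatory biomarkers (e.g. hsCRP, IL-6) and cognitive function (MoCA". The synopsis lists the matching analysis among the exploratory outcomes: "Correlation analysis between MoCA scores and inflammatory biomarker levels with and without adjusting for hemorrhage burden (Hijdra Sum Score". Hijdra is the only covariate it names.

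Section 10.2 describes three analyses and does not rank them:

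- pooled over both arms: "testing the correlations with one sample (treatment + control groups together), we can identify an absolute correlation of 0.27 from no correlation";
- by arm: "When comparing within each treatment group the detectable correlation will be at least 0.37";
- between arms: "For comparing correlations between two groups (treatment and controls), the difference of detectable correlation is at least 0.50 at the same design parameters".

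The protocol expects heparin to act on both variables. Secondary objective 2 is: "Demonstrate a reduction in blood / CSF levels of inflammatory biomarkers (e.g. hsCRP, IL-6) in the LDIVH treated subjects compared to controls". For MoCA, Table S1 in section 10.1 has: "Sample sizes based on having alpha=5% and SD1=7.0 and SD2=2.5 to detect 3 unit (effect size=0.5 SD", with the lower spread in the treatment arm.

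**The concern.** The pooled analysis is meant to show whether inflammation tracks cognition. If treatment moves both variables, patients in the LDIVH arm tend to have lower biomarker values and higher MoCA scores, and control patients the reverse. The two arm means then produce a negative pooled correlation with no biomarker–MoCA relation within either arm. The test partly repeats the two treatment comparisons and does not isolate objective 1.

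The spurious signal points in the hypothesized direction and appears when the drug works on both measures. Adjusting for Hijdra does not remove it: Hijdra grades the blood on the admission CT, which randomization balances in expectation, so it cannot account for a difference that treatment creates later. At stake is how the mechanistic result is read in a trial meant to inform a Phase III decision.

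**Working it through.** **Inputs.** From section 10.1: 40 evaluable and 44 enrolled per arm, MoCA difference 3 points, SD 7.0 (control) and 2.5 (LDIVH), alpha 5%, power 80%. The protocol gives no size for the biomarker reduction, so the shift dB, in within-arm SD units, is an assumption. The main range shown is 0.5 to 1.0.

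**Step 1: the plan's own figures.** By Fisher's z, with one-sided 5% and 80% power, the detectable r is tanh((1.645 + 0.842)/√(N − 3)).

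- N = 80: tanh(2.487/√77) = 0.276. N = 88: tanh(2.487/√85) = 0.263. These bracket the stated 0.27.
- 44 in one arm: tanh(2.487/√41) = 0.370, as stated.
- Difference between arms, 44 each: tanh(2.487 × √(2/41)) = 0.50, as stated.

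Two-sided tests give 0.309 (N = 80) and 0.295 (N = 88) for the pooled case and do not reproduce 0.27. So the figures come from one-sided tests, and the pooled calculation has no term for arm.

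**Step 2: the correlation induced by the arm means.** With equal arms and zero within-arm correlation, the size of the pooled correlation is

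r = 0.25 × dM × dB / √[(V + 0.25 × dM²)(1 + 0.25 × dB²)],

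where dM = 3 and V = (7.0² + 2.5²)/2 = 27.625, so V + 0.25 × 9 = 29.875. Its sign is negative.

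- dB = 0.5: 0.375/√(29.875 × 1.0625) = 0.067
- dB = 0.8: 0.600/√(29.875 × 1.16) = 0.102
- dB = 1.0: 0.750/√(29.875 × 1.25) = 0.123

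However large dB is, r cannot exceed 1.5/√29.875 = 0.274.

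**Step 3: rejection rates.** Simulation with 20,000 trials per setting, 40 per arm, zero within-arm correlation, nominal 5%:

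| Biomarker shift (SD) | Pooled, one-sided | Pooled, two-sided | Arm-adjusted, one-sided |
|---|---|---|---|
| 0 | 5.2% | 5.0% | 5.1% |
| 0.25 | 8.9% | 6.1% | 5.1% |
| 0.5 | 14.7% | 8.7% | 4.8% |
| 0.8 | 23.2% | 14.8% | 5.3% |
| 1.0 | 29.3% | 19.8% | 5.2% |
| 2.0 | 55.1% | 42.3% | 5.0% |

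With the pilot MoCA difference (26.4 − 22.7 = 3.7), the pooled one-sided rates at 0.5, 0.8 and 1.0 SD are 17.7%, 29.8% and 38.1%. Correlations computed within a single arm reject at about 5% throughout.

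**Step 4: price of the adjustment.** One degree of freedom fewer at 80 patients gives tanh(2.487/√76) = 0.278, against 0.276.

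**The case against.** Much can be said for the plan as it stands.

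- A reader might infer that objective 1 is tested only on the pooled sample. It is not: 10.2 also plans within-arm correlations and a comparison between arms, neither open to this problem. A pooled correlation made only by arm means would sit beside within-arm estimates near zero. This stands, and limits the point to one analysis of three. What remains is that the pooled test is the most sensitive of the three (0.27 against 0.37) and that no rule says which governs if they disagree.
- Covariates for an exploratory correlation may be left to a statistical analysis plan, and sections 10.1 and 10.4 foresee multivariable models. That is fair, but the point is not an omitted detail. Section 10.2 fixes a pooled test and sizes it without arm, the synopsis names its adjustment without arm, and the modelling language elsewhere does not add it here.
- The synopsis asks about any association in aSAH, and a pooled correlation does estimate the marginal association in the trial sample. On that reading the induced correlation is real. But it then reflects treatment acting on two variables, and says nothing about whether they are linked to each other.
- The size is conditional. The one-sided rule in 10.1 ("MoCA is higher in the treatment arm than in the control arm, and so we will use one-sided test procedures") is written for the treatment comparison; for the correlation it is inferred from step 1. The 3-point difference is for 90 days, whereas sections 3 and 6.12.6 also pair biomarkers with inpatient MoCA, for which no treatment difference is assumed. All of this stands.

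**Conclusion.** The pooled, arm-unadjusted correlation in 10.2 does not keep its nominal error rate against the hypothesis of no within-arm association when the trial's own treatment hypotheses hold. For assumed biomarker shifts of 0.5 to 1.0 SD, rejection is roughly 3 to 6 times nominal one-sided and 2 to 4 times two-sided. This rests on a true 3-point difference in 90-day MoCA with the design SDs, 40 patients per arm, zero within-arm correlation, and a biomarker shift that the protocol does not supply.

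Two stronger readings are not supported. A reader might infer that the test will find a correlation: the induced r is well below the stated detectable 0.27, and at shifts of 0.5 to 1.0 SD most such trials would not reject. A reader might also infer that the trial's main conclusions are compromised. They are not: study success in the synopsis depends on mean MoCA or biomarker reduction together with bleeding, and the correlation enters neither that rule nor the primary comparison. This is a worthwhile, nearly free improvement to a secondary objective.

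**What to change.** In 10.2 and the synopsis:

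- Test the all-patient biomarker–MoCA association with treatment arm as a covariate, by partial correlation or by regression of MoCA on the biomarker and arm, each with and without the Hijdra score.
- Restate the detectable correlation as about 0.28 at 80 patients.
- Report any unadjusted pooled correlation as description only.
- Keep the planned within-arm correlations and the between-arm comparison.

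The cost is a wording change and one degree of freedom. Arm is known for every randomized patient, so the adjustment loses no one from the analysis.

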1. STUDY SYNOPSIS AND OBJECTIVES

1.1 STUDY SYNOPSIS

STUDY TITLE	Aneurysmal Subarachnoid hemorrhage Trial RandOmizing Heparin (ASTROH)
PRIMARY OBJECTIVES	The primary objective of this study is to investigate the safety and clinical effect of a continuous low-dose intravenous unfractionated heparin (LDIVH) infusion for the prevention of aneurysmal subarachnoid hemorrhage (aSAH) induced neurocognitive dysfunction. The rate of “Major Bleeding” or “Clinically Relevant Non-Major Bleeding” as defined by the International Society of Thrombosis and Haemostasis (ISTH) between the LDIVH and the control group will be compared. The mean Montreal Cognitive Assessment (MoCA) scores obtained at a 90-day follow-up visit will be compared between LDIVH treated patients and controls. We expect the results of this study to inform on whether a properly powered Phase III study evaluating a LDIVH infusion for aSAH is warranted.
SECONDARY OBJECTIVES	Increased blood and CSF levels of certain inflammatory biomarkers have been correlated to aSAH patients with poor clinical outcomes. Unfractionated heparin (UFH) has known anti-inflammatory actions. As a result, a secondary objective of this study will be to evaluate whether LDIVH can reduce blood and CSF inflammatory biomarker levels compared to controls and whether there is any association between inflammatory biomarker levels and cognitive outcomes in aSAH.
STUDY DESIGN	Investigator initiated and sponsored, multicenter, prospective, 1:1 randomized, open-label, blinded adjudication phase II study. Study patients randomized to the LDIVH arm will receive normal standard of care (SOC) plus a continuous low-dose intravenous infusion of UFH for up to 14 days. During the 14-day infusion, the LDIVH arm study subjects will not receive any chemical deep venous thrombosis

	
(DVT) prophylaxis but may resume chemical DVT prophylaxis after the 14-day infusion is complete. Study patients randomized to the control arm will receive the normal standard of care (SOC), which will be UFH 5,000 units, twice daily.

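### The detectable correlations in Section 10.2 rest on the one-sided 5% level carried over from the MoCA comparison, although the question is worded without direction; the between-arm figure also needs enrolled rather than evaluable numbers

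*Protocol*

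**What the plan says.** Protocol Section 10.1 fixes the design parameters. It argues from pilot data that "MoCA is higher in the treatment arm than in the control arm, and so we will use one-sided test procedures". Table S1 is headed "Sample sizes based on having alpha=5% and SD1=7.0 and SD2=2.5 to detect 3 unit" with a one-sided t test, and its 80% power row gives 40 per arm. The plan follows that row: "we plan to enroll 40 evaluable subjects in each arm". With 10% dropout, "the trial would require 44 patients in each arm for a total enrollment plan of 88 patients". The supporting binomial calculation is also one-sided: "This will also allow a demonstration of power = 80% with alpha at 0.05 for our previously calculated sample sizes".

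Section 10.2 then states that "we can identify an absolute correlation of 0.27 from no correlation at the same design parameters", meaning both arms pooled. It gives 0.37 within each arm and 0.50 for the difference between the two arms' correlations. It refers back to the Section 10.1 parameters without restating alpha, sidedness, power or n, and for the method it cites only two textbooks.

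The question these figures serve is worded without direction. The synopsis (Section 1.1) asks "whether there is any association between inflammatory biomarker levels and cognitive outcomes in aSAH", and the first objective in Section 1.2.2 is simply to measure the correlation. Section 10.4 sets a 5% significance level and does not say whether it is one- or two-sided.

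**The concern.** An absolute correlation, or any association, is a claim about size in either direction, and the natural test is two-sided. The protocol's reason for one-sided testing is that mean MoCA should be higher on heparin. That says nothing about the sign of a biomarker-MoCA correlation, and still less about which arm should show the larger one. If the figures were computed one-sided, Section 10.2 claims more sensitivity than a two-sided 5% test provides. A null correlation result would then be read as more informative than it is.

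**Working it through.** **Inputs.** Alpha 5%, one-sided, 80% power, 40 evaluable per arm (80 pooled), 44 enrolled per arm (88 pooled), all from Section 10.1. The stated figures 0.27, 0.37 and 0.50 are from Section 10.2. Normal quantiles: 1.645 (one-sided 5%), 1.960 (two-sided 5%), 0.842 (80% power). The sums are about 2.487 one-sided and 2.802 two-sided.

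**Formulas.**
- One correlation, Fisher z: r = tanh[(z_alpha + z_power)/√(n − 3)].
- Difference between arms, Fisher z, with one arm's correlation zero: tanh[(z_alpha + z_power)·√(2/(n − 3))], n per arm.
- One correlation, noncentral t: n − 2 degrees of freedom, noncentrality r√n/√(1 − r²), solved for 80% power.

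**Step 1: reproduce the stated figures, one-sided 5%, 80% power.**

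| Method and n | Pooled | Within arm | Difference |
|---|---|---|---|
| Stated in 10.2 | 0.27 | 0.37 | 0.50 |
| Noncentral t, 80/40 | 0.270 | 0.372 | – |
| Fisher z, 80/40 | 0.276 | 0.387 | 0.521 |
| Fisher z, 88/44 | 0.263 | 0.370 | 0.500 |

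Example: tanh(2.487 × √(2/41)) = tanh(0.549) = 0.500. All three figures can be reached one-sided. The 0.50 appears only with 44 per arm; with 40 it is 0.52.

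**Step 2: the same at two-sided 5%, 80% power.**

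| Method and n | Pooled | Within arm | Difference |
|---|---|---|---|
| Noncentral t, 80/40 | 0.302 | 0.414 | – |
| Fisher z, 80/40 | 0.309 | 0.431 | 0.573 |
| Noncentral t, 88/44 | 0.289 | 0.397 | – |
| Fisher z, 88/44 | 0.295 | 0.412 | 0.550 |

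The smallest two-sided values, even with every enrolled patient analysed, are 0.289, 0.397 and 0.550. None of the methods tried reproduces a stated figure two-sided at 80% power.

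**Step 3: separate the two causes.** By Fisher z with n held at 44 per arm, sidedness alone moves 0.37 to 0.41 and 0.50 to 0.55. Using the 40 evaluable takes these on to 0.43 and 0.57.

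**Step 4: power at the stated values, two-sided 5%, Fisher z.** Power = Φ(atanh(r)/SE − 1.960), where SE is 1/√(n − 3) for one correlation and √(2/(n − 3)) for the difference.
- 40 per arm: 68% at 0.27, 66% at 0.37, 66% at 0.50.
- 44 per arm: 72%, 70% and 70%.

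Example: atanh(0.37) × √37 = 0.388 × 6.083 = 2.363; 2.363 − 1.960 = 0.403; Φ(0.403) = 0.656.

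Keeping the stated figures at two-sided 5% and 80% power would need 106 patients pooled for 0.27, and 56 per arm for each of 0.37 and 0.50.

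**The case against.** **A direction is implied.** The synopsis links raised biomarker levels to poor clinical outcome, and Section 2.1 says that elevated IL-6 and hs-CRP predict it. Low MoCA is the bad direction, so the expected correlation is negative, and *absolute* may mean only the size of a negative number. On that reading, one-sided 0.27 and 0.37 agree with Section 10.1. This stands in part. A directional hypothesis could have been written for the pooled and within-arm tests, but it was not, and the wording points the other way. It gives no direction for the between-arm difference.

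**Sidedness is inferred.** Section 10.2 does not state it, and no single method and n tried gives all three figures exactly. Two-sided 5% with 70% power and 44 per arm gives 0.263, 0.370 and 0.500. But 70% power appears nowhere in the protocol: Table S1 lists 80%, 85% and 90%, and the chosen n is its 80% row. The inference is strong, though not certain.

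**It belongs in the SAP.** The test rule may well be there. The printed figures and their wording are in the protocol.

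**It matters little.** Section 10.2 concludes only that detectable effects are moderate to large, and that survives. The synopsis lists the MoCA-biomarker correlation among exploratory analyses, although Section 1.2.2 makes it a secondary objective. This limits the weight of the point.

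**Conclusion.** The point holds as a defect in a sensitivity statement. At 80% power the three figures arise only one-sided, while the question is worded without direction and the reason given for one-sidedness does not carry over. The case is clearest for the between-arm 0.50, which has no directional basis, uses enrolled rather than evaluable numbers, and assumes a zero correlation in one arm. At two-sided 5% the real power at the stated values is about 66-68% with 40 per arm, or 70-72% with 44. This rests on reading the back-reference in Section 10.2 as one-sided 5% and 80% power, and on normal-theory approximations.

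Two stronger readings are not supported. A reader might infer that correlations in either direction will be declared significant at a true 10% error rate. The protocol states no such rule: Section 10.2 is a sensitivity calculation, and Section 10.4 gives 5% without sidedness. A reader might also infer that all three figures are simply wrong, and that sidedness explains the whole gap to 0.43 and 0.57. The pooled and within-arm figures could be defended under a stated negative direction, and part of the gap comes from moving from 44 to 40 per arm.

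**What to change.** In Section 10.2, state the sidedness, the n and the method. Restate the detectable values at two-sided 5%, 80% power and 40 evaluable per arm:
- pooled: about 0.30 (noncentral t) to 0.31 (Fisher z);
- within arm: about 0.41 to 0.43;
- difference between arms: about 0.57, stating that one correlation is taken as zero.

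Alternatively, for the pooled and within-arm tests only, state and justify a negative direction, drop the word *absolute*, and keep about 0.27 and 0.37-0.39. The between-arm figure should be two-sided in either case.

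The cost is three figures and a sentence or two, and the stated sensitivity becomes slightly less favourable. The sample size, the primary test and trial conduct are untouched.
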